6.5. Visit Windows

Visits specified in the electronic case report form (eCRF) will be used for this study. Measurements will be performed according to the Time and Events Schedule in protocol Appendix 1. The acceptable time deviations relative to the time points specified in protocol Appendix 1 are shown in Table 6-1. Every effort will be made to adhere as closely as possible to the procedure time points specified.

Table 6-1 Acceptable Time Windows

Study Activity	Time Points		Acceptable Time Window
Screening	Can be Treatment Day 1		Within 4 days prior to Treatment Day 1
Enrollment	Treatment Day 1		---
Drug infusion	See Appendix 1		± 15 minutes
Dosing interval	See Appendix 1		± 15 minutes
Pharmacokinetic blood sampling	Cohorts 1 and 2	1 hour after start of infusion	± 15 minutes
		3 hours after start of infusion	Within 15 minutes prior to the end of infusion using a separate line or immediately after the end of infusion using the same line and with proper flushing
		3.5 hours after start of infusion	± 15 minutes
		5 and 8 hours after start of infusion	± 30 minutes
	Cohorts 3 and 4	3 hours after start of infusion	Within 15 minutes prior to end of infusion using a separate line or immediately after the end of infusion using the same line and with proper flushing
		5 and 8 hours after start of infusion	± 30 minutes
EOT	Within 24 hours after last day of study treatment		As soon as possible after last dose (same calendar day)
Posttreatment	7 days after EOT		± 4 days
EOS	28 days after last dose of study treatment		+ 7 days

EOS = End of Study; EOT = End of Treatment

EOS = End of Study; EOT = End of Treatment.

This document is confidential.

All the data, including unscheduled visits, will be included in the listings. If multiple records exist at the same visit/time point, the closest record to target day will be used for the purpose of summary tables. If these are some records that have the same difference from the target day, the latest record will be used.

This document is confidential.

7. Demographic, Other Baseline Characteristics, and Medication

7.1. Subject Disposition and Withdrawals

The number of subjects screened, screen failed, and enrolled will be summarized.

A summary table will be produced detailing the number and percentages of all subjects who are enrolled, subjects in each analysis populations, subjects who received study drug (cefiderocol), subjects who completed study drug, subjects who discontinued study drug, subjects who completed the study and subjects who prematurely discontinued the study. In addition, reasons leading to discontinuation from study and study drug discontinuation will be summarized for each cohort and overall. A listing of subject disposition, and a separate listing of subjects that discontinued or withdraw early will also be provided.

The number and proportion of subjects included in each analysis population and the reasons for exclusion will also be presented. A listing of subjects excluded from each analysis population will also be produced.

7.2. Demographic and Other Baseline Characteristics

Demographic and baseline characteristics, including date of birth, age (in months as collected on the Demographics eCRF), age in years, sex, race, ethnicity, height (cm), weight (kg), body mass index (kg/m^2), and eGFR (mL/min/1.73 m^2), will be summarized by cohort using standard descriptive statistics for the Safety, ITT, and MITT Populations. Infection type (complicated urinary tract infection [cUTI], pneumonia, complicated intra-abdominal infection [cIAI], hospital-acquired pneumonia [HAP]/ventilator-acquired pneumonia [VAP], sepsis or bloodstream infections [BSI], other) will be summarized by single and multiple dose phases. In addition, for subjects in multiple dose phase, these parameters will be summarized by treatment regimen (cefiderocol alone or cefiderocol + SOC) for ITT and MITT Population.

The baseline Gram-negative pathogen will be summarized by cohort groups and baseline infection site for the MITT Population. In addition, baseline Gram-negative pathogen will be summarized by cohort groups and treatment regimen (cefiderocol alone or cefiderocol + SOC) for ITT and MITT Population.

The baseline pathogen will also be summarized for the MIC values, and susceptibility will be defined by Clinical and Laboratory Standards Institute (CLSI) and European Committee on Antimicrobial Susceptibility Testing (EUCAST) of the baseline pathogen. For this analysis, the MIC for cefiderocol, amikacin, aztreonam, ceftazidime-avibactam, imipenem, ceftolozanetazobactam, ciprofloxacin, meropenem, cefepime, colistin, and tigecycline will be used, and the number of subjects, MIC_{50} , MIC_{90} , and range will be calculated for summary statistics of MIC. MIC_{50} and MIC_{90} will be defined as the smallest value no less than 50% and 90% of the data, respectively; MIC_{50} and MIC_{90} will be calculated only when the number of subjects with a particular bacterium is 10 or more.

Body mass index (BMI) is calculated as follows:

$$\text{BMI (kg/m}^2\text{)} = \text{Weight(kg)}/[\text{Height(m)}^2]$$

Age in years is calculated as follows:

$$\text{Age (years)} = (\text{Age in months collected in eCRF})/12 \text{ and rounded up to one decimal place.}$$

Demographics and informed consent data will be listed by subject for all the subjects.

This document is confidential.

7.3. Inclusion/Exclusion Criteria

All inclusion/exclusion criteria definitions will be listed. Inclusion/exclusion criteria deviations will be listed by subject.

7.4. Medical History

Medical history will be summarized for the MITT and Safety Populations by MedDRA System Organ Class (SOC) and Preferred Term (PT). The reported medical history terms will be coded using Medical Dictionary for Regulatory Activities (MedDRA) Version 23.0 or higher.

Medical history findings will be listed by subject using the Safety and MITT Populations.

7.5. Prior and Concomitant Therapies

The original verbatim terms of the prior and concomitant therapies collected in the eCRF will be coded using the World Health Organization (WHO) Drug Dictionary, Version Sep. 2019.

In the event of a missing start date or time associated with a therapy, prior/concomitant therapy will be determined by imputation using the algorithm described in Section 6.4.1.

Prior and concomitant therapies will be listed and summarized for the Safety Population. Prior and concomitant therapy data will be listed chronologically by subject and will include the data collected in the eCRF, along with the coded variables. For the summary tables, the number and percentage of subjects under each preferred drug or procedure name will be summarized by cohort. If a subject has taken 1 or more prior or concomitant medications more than once, the subject will be counted only once during any given drug class. Prior and Concomitant Therapies will be summarized by antibiotic therapy, standard of care treatment for disease and non-antibiotic therapy using the Safety Population.

7.5.1. Prior Therapy

Prior antibiotic therapy is defined as any antibiotic administered for current infection. Prior therapy (Prior antibiotic therapy, Prior Standard of Care Treatment for Disease, Prior Non-Antibiotic therapy) is defined as any therapy administered within 14 days prior to administration of the first dose of cefiderocol.

7.5.2. Concomitant Therapy

Concomitant therapy (Concomitant antibiotic therapy, Concomitant Standard of Care Treatment for Disease, Concomitant Non-Antibiotic therapy) is defined as any therapy administered after study drug is administered in the study.

This document is confidential.

8. Efficacy

Efficacy endpoints will be evaluated for subjects in the multiple-dose phase of the study for the ITT and MITT analysis Populations.

The efficacy endpoints are as follows:

- Clinical outcome, defined as the categories below:

HAP/VAP/cIAI:

- Clinical Cure: Resolution or substantial improvement of baseline signs and symptoms of pneumonia/cIAI.
- Clinical Failure: No apparent response to therapy; persistence or worsening of baseline signs and/or symptoms of pneumonia/cIAI; reappearance of signs and/or symptoms of pneumonia/cIAI; development of new signs and/or symptoms of pneumonia/cIAI requiring antibiotic therapy other than, or in addition to, study drug therapy; progression of chest radiographic abnormalities; or death due to pneumonia/cIAI.
- Indeterminate: Lost to follow-up such that a determination of clinical cure/failure cannot be made.

cUTI:

- Clinical Cure: Resolution or substantial improvement of baseline signs and symptoms of cUTI, or return to pre-infection baseline if known, such that no antibiotic therapy is required for the treatment of the current infection.
- Clinical Failure: No apparent response to therapy; persistence or worsening of baseline signs and/or symptoms of cUTI; or reappearance of signs and/or symptoms of cUTI; development of new signs and/or symptoms of cUTI requiring antibiotic therapy other than, or in addition to, study drug therapy; or death due to cUTI.
- Indeterminate: Lost to follow-up such that a determination of clinical cure/failure cannot be made.

BSI/Sepsis:

- Clinical Cure: Resolution or substantial improvement of baseline signs and symptoms. Subjects with bacteremia must have eradication of bacteremia caused by the Gram-negative pathogen.
- Clinical Failure: No apparent response to therapy; persistence or worsening of baseline signs and/or symptoms, reappearance of signs and/or symptoms; development of new signs and/or symptoms requiring antibiotic therapy other than, or in addition to, study drug therapy; or death due to BSI/sepsis.
- Indeterminate: Lost to follow-up such that a determination of clinical cure/failure cannot be made.

This document is confidential.

- Microbiological outcome per pathogen defined as the categories below:

HAP/VAP/cIAI and BSI/Sepsis:

- Persistence: Continued presence of the baseline Gram-negative pathogen from an appropriate clinical specimen.
- Indeterminate: No culture obtained from an appropriate clinical specimen or additional antibiotic therapy for the treatment of the current infection including missed sampling for reasons other than a successful clinical outcome.
- Eradication: Absence of the baseline Gram-negative pathogen from an appropriate clinical specimen. If it is not possible to obtain an appropriate clinical culture and the subject has a successful clinical outcome, the response will be presumed to be eradication.

cUTI:

- Persistence: A urine culture shows that the baseline Gram-negative uropathogen found at entry at $\geq 10^5$ CFU/mL grows to $\geq 10^3$ CFU/mL.
- Indeterminate: No urine culture obtained or additional antibiotic therapy for the treatment of the current infection including missed sampling.
- Eradication: A urine culture shows that the baseline Gram-negative uropathogen found at entry at $\geq 10^5$ colony forming units (CFU)/mL is reduced to $< 10^3$ CFU/mL.

Clinical response will be characterized based on an evaluation of clinical signs and symptoms by the investigator or designee. Clinical outcomes will be characterized at EOT, Posttreatment, and EOS if available.

The microbiological outcomes per subject determined by investigator will be entered in the eCRF. When the investigator confirms:

- that the subject experiences eradication of all baseline Gram negative pathogens then “Eradication” will be entered. For subjects with baseline infection other than cUTI who achieved clinical cure at corresponding visit, the response will be considered as Eradicated.
- that the subject experiences persistence of any baseline Gram-negative pathogen then “Persistence” will be entered
- that the subject experiences anything other than above then “Indeterminate” will be entered.

Emergent (ie, nonbaseline) pathogens will be considered separately, and will not affect the per-subject microbiological outcome.

This document is confidential.

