Blood samples for determination of plasma cefiderocol concentrations will be collected from each subject at prespecified time points during and/or after the cefiderocol infusion ([Section 7.4](#)). Cefiderocol PK will be determined in the single-dose phase in each of the cohorts; cefiderocol dose recommendations may be revised by the sponsor prior to initiating enrollment of subjects in the multiple-dose phase of each respective cohort.

In the multiple-dose phase only, clinical outcome data and microbiological outcome data will be obtained. Clinical and microbiological outcome assessments will be performed at EOT, at the Posttreatment visit (7 \pm 4 days after EOT), and EOS if available. Data from assessments performed prior to, during, and after treatment with SOC antibiotics as part of routine patient care will be captured as study data. The time points for collection of microbiological specimens are otherwise not prespecified by the protocol (Posttreatment Visit, EOT, and EOS, if available; [Section 7.6](#)). In subjects where it is not possible to obtain a posttreatment culture and/or EOS culture, determination of presumed microbiological eradication may be made based on resolution of all presenting clinical sign and symptoms of the infection (clinical cure).

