7.6.1.1.3 BSI/Sepsis

- **Clinical Cure:** Resolution or substantial improvement of baseline signs and symptoms. Subjects with bacteremia must have eradication of bacteremia caused by the Gram-negative pathogen.
- **Clinical Failure:** No apparent response to therapy; persistence or worsening of baseline signs and/or symptoms, reappearance of signs and/or symptoms; development of new signs and/or symptoms requiring antibiotic therapy other than, or in addition to, study treatment therapy; or death due to BSI/sepsis.
- **Indeterminate:** Lost to follow-up such that a determination of clinical cure/failure cannot be made.

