7.6.2.1.1 HAP/VAP/cIAI and BSI/Sepsis

- **Eradication:** Absence of the baseline Gram-negative pathogen from an appropriate clinical specimen. If it is not possible to obtain an appropriate clinical culture and the subject has a successful clinical outcome, the response will be presumed to be eradication.
- **Persistence:** Continued presence of the baseline Gram-negative pathogen from an appropriate clinical specimen.
- **Indeterminate:** No culture obtained from an appropriate clinical specimen or additional antibiotic therapy for the treatment of the current infection including missed sampling.

7.6.2.1.2 cUTI

- **Eradication:** A urine culture shows the baseline Gram-negative uropathogen found at entry at $\geq 10^5$ colony forming units (CFU)/mL are reduced to $< 10^3$ CFU/mL.
- **Persistence:** A urine culture shows that the baseline Gram-negative uropathogen found at entry at $\geq 10^5$ CFU/mL grows $\geq 10^3$ CFU/mL.

- **Indeterminate:** No urine culture obtained or additional antibiotic therapy for the treatment of the current infection including missed sampling.

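### The SAP's per-subject microbiological rule omits the condition that no culture could be obtained, so a cured but culture-positive subject falls into two categories with no order of precedence

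*SAP*

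**What the plan says.** SAP Section 8 defines the microbiological outcome twice, per pathogen and per subject.

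- **Per pathogen, HAP/VAP/cIAI and BSI/sepsis.** Persistence is "Continued presence of the baseline Gram-negative pathogen from an appropriate clinical specimen", with no reference to clinical outcome. Eradication is absence of the pathogen, with one allowance: it is presumed when no suitable culture can be had and the clinical result is a success.
- **Per subject.** The item for Eradication requires all baseline Gram-negative pathogens to be eradicated, then adds: "For subjects with baseline infection other than cUTI who achieved clinical cure at corresponding visit, the response will be considered as Eradicated". The next item says that when the investigator confirms "that the subject experiences persistence of any baseline Gram-negative pathogen then" the entry is Persistence.

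Protocol 7.6.2.1.1 allows presumed eradication on the same terms as the SAP's per-pathogen rule: "If it is not possible to obtain an appropriate clinical culture and the subject has a successful clinical outcome". Protocol 3.1 and the footnotes to Protocol Appendix 1 also confine it to subjects without an obtainable culture. Protocol 7.6.2.1 builds the per-subject outcome from the outcomes of the individual baseline pathogens.

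Protocol 9.1 says that reasons for departing from the protocol's analyses will be given in the SAP. SAP Section 12 reports no departures.

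**The concern.** The sentence in the per-subject list turns a rule for missing cultures into a rule for all cultures. Outside cUTI, clinical cure alone is enough for the subject to count as Eradicated, whatever the laboratory reports. The outcome is then no longer built from the per-pathogen results, as Protocol 7.6.2.1 requires, and a programmer cannot tell which of two adjacent items governs a subject who is cured and culture-positive.

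At stake is the microbiological half of the secondary objective (cefiderocol alone) and the matching exploratory summaries. The planned per-subject table (14.2.1.4.1) and per-pathogen table (14.2.1.5) could disagree about the same subject at the same visit. In an open-label study whose SAP may be revised with data in view (Protocol 9.1), the order of precedence should be settled before outcomes are tabulated.

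**Working it through.** **Denominator.** SAP 3.4 gives a minimum of 10 subjects in each of three multiple-dose cohorts: 3 × 10 = 30, which agrees with the stated total. These are minimum enrolment figures. The microbiological tables use the MITT population, a subset, and the cefiderocol-alone group is smaller again, so 10 and 30 are guides only.

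**Classification.** Take one baseline pathogen, one visit, and an infection other than cUTI whose cure definition rests on signs and symptoms alone.

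| Clinical outcome | Culture | Per-pathogen and protocol rule | Per subject, added sentence read literally | Per subject, Persistence item first |
|---|---|---|---|---|
| Cure | Negative | Eradication | Eradication | Eradication |
| Cure | **Positive** | **Persistence** | **Eradication** | **Persistence** |
| Cure | Not obtainable | Eradication (presumed) | Eradication | Eradication |
| Failure | Negative | Eradication | Eradication | Eradication |
| Failure | Positive | Persistence | Persistence | Persistence |
| Failure | Not obtainable | Indeterminate | Indeterminate | Indeterminate |

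One row differs, and it differs upward. If the Persistence item takes precedence, no row differs.

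**Where that row can occur.**

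- *HAP/VAP and cIAI:* yes. Cure is resolution or substantial improvement of signs and symptoms. SAP 6.2.3 lists blood as the cIAI specimen, and cIAI cure has no blood-clearance condition.
- *BSI/sepsis with bacteraemia, judged on blood:* no. "Subjects with bacteremia must have eradication of bacteremia caused by the Gram-negative pathogen" before cure can be declared.
- *Sepsis without bacteraemia:* yes, if the organism came from another specimen accepted as appropriate.
- *Other infections:* yes, on the assumption that the general non-cUTI definitions are applied. Section 8 gives this group none of its own.
- *cUTI:* no. The sentence excludes it.

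**Size per discordant subject.** Overstatement = 100 × k/N points, where k is the number of cured, culture-positive subjects.

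| N | k = 1 | k = 2 | k = 3 |
|---|---|---|---|
| 5 | 20.0 | 40.0 | 60.0 |
| 10 | 10.0 | 20.0 | 30.0 |
| 20 | 5.0 | 10.0 | 15.0 |
| 30 | 3.3 | 6.7 | 10.0 |

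**Illustration on assumed rates.** The documents give no rate for k. Let f be the share of subjects with a susceptible infection type (neither cUTI nor bacteraemia), c the clinical cure rate (0.80) and q the share of cured subjects with a positive culture. Expected overstatement = 100·f·c·q, and the chance of at least one such subject among 30 is 1 − (1 − f·c·q)^30.

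- q = 0, any f: 0 points; chance 0.
- f = 0.3, q = 0.05: 100 × 0.3 × 0.8 × 0.05 = 1.2 points; chance 0.30.
- f = 0.5, q = 0.10: 100 × 0.5 × 0.8 × 0.10 = 4.0 points; chance 0.71.
- f = 0.7, q = 0.20: 100 × 0.7 × 0.8 × 0.20 = 11.2 points; chance 0.97.

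A literal reading could also turn an Indeterminate caused by additional antibiotic therapy into Eradication. That is not modelled, but it too would raise the rate.

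**The case against.** The strongest reply is that no SAP text says a cured subject is Eradicated despite a positive culture. The sentence sits inside the Eradication item and can be taken as shorthand for the presumption rule a few lines above, which keeps the no-culture condition. The next item then deals with persistence of any baseline pathogen. On that reading nothing is overstated. This stands as a possible reading, and it is why the defect is an unresolved conflict rather than a settled error. It does not remove the conflict: the SAP gives no order between the items. One describes what the investigator enters and the other how the response is considered, so the second can equally be read as an analysis rule laid over the entry.

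The stakes are also limited. Protocol 7.7 treats efficacy as supplementary and deliberately not rigorous, the sample size ignores it, and SAP 6.1 rules out inferential testing. Follow-up specimens are taken only where possible and clinically indicated, so cured, culture-positive subjects may be few or absent. Per-pathogen outcomes are tabulated and microbiology is listed, so a discrepancy could be found. Missing and indeterminate outcomes count as non-response (SAP 6.4.2), and SAP 8.1.2 warns of underestimation from missing EOS data. All of this stands and lowers the severity. The last point is a separate bias, though, and does not offset this one in any known proportion.

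**Conclusion.** The concern holds as a drafting conflict with a possible one-way effect. The per-subject sentence omits a condition found in the SAP's own per-pathogen definition and in the protocol, the neighbouring item contradicts it for cured, culture-positive subjects, and SAP Section 12 does not declare the departure. If the sentence is applied literally, per-subject eradication rises by 10 points per discordant subject at N = 10 and 3.3 at N = 30. The number of such subjects is unknown and may be zero. Severity is minor to moderate.

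Three stronger inferences are tempting but are not supported:

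- *That the rule inflates eradication in every infection except cUTI.* In BSI/sepsis with bacteraemia judged on blood, cure already requires eradication. The protocol has the same pairing, so this is not a SAP departure.
- *That the microbiological endpoint becomes a copy of the investigator's clinical judgement.* Subjects without clinical cure are still classified by culture, and the per-pathogen results do not pass through the sentence.
- *That the SAP loosened the clinical trigger.* Protocol 3.1 makes the presumption "based on resolution of all presenting clinical sign and symptoms of the infection (clinical cure"), while Protocol 7.6.2.1.1 asks only for a successful clinical outcome and Protocol 7.6.1.1.1 counts substantial improvement as cure. That tension lies within the protocol; the SAP copies the cure definitions.

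**What to change.** In SAP Section 8, make two changes to the per-subject list:

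1. Limit the added sentence to the protocol's condition, applied visit by visit: for infections other than cUTI, presume eradication only "If it is not possible to obtain an appropriate clinical culture and the subject has a successful clinical outcome".
2. State that a positive culture for any baseline Gram-negative pathogen is Persistence and takes precedence over clinical cure.

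Optionally, show documented and presumed eradication as separate rows. Neither document requires this, but it would show how much of the rate rests on clinical outcome.

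Reconcile the two protocol descriptions of the clinical basis for presumption (3.1 and 7.6.2.1.1) rather than writing a third, stricter one into the SAP. In particular, do not remove presumed eradication for bacteraemia, since Protocol 7.6.2.1.1 expressly covers BSI/sepsis.

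If the sponsor does intend clinical cure to override a positive culture, SAP Section 12 should say so and give the reason.

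The cost is one clause, one derivation and, if wanted, one table row. Reported eradication rates may be slightly lower. Classification is unchanged for cUTI, for cured subjects with a negative or unobtainable culture, and for bacteraemia judged on blood.
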